1. Antelope Valley Health Center, [name]
2. Bell Health Center, [name]
3. Bellflower Health Center, [name]
4. Curtis R. Tucker Health Center, [name]
5. East Los Angeles Health Center, [name]
6. East San Gabriel Valley Health Center, [name]
7. Edward Roybal Comprehensive Health Center, [name]
8. El Monte Comprehensive Health Center, [name]
9. Glendale Health Center, [name]
10. H. Claude Hudson Comprehensive Health Center, [name]
11. Harbor-UCLA Medical Center, [name]
12. High Desert Regional Health Center, [name]
13. Hubert H Humphrey Comprehensive Health Center, [name]
14. La Puente Health Center, [name]
15. LAC+USC Medical Center, [name]
16. Lake Los Angeles Community Clinic, [name]
17. Littlerock Community Clinic, [name]
18. Long Beach Comprehensive Health Center, [name]
19. Martin Luther King, Jr. Outpatient Center, [name]
20. Mid-Valley Comprehensive Health Center, [name]
21. North East Health Center, [name]
22. Olive View-UCLA Medical Center, [name]
23. Rancho Los Amigos National Rehabilitation Center, [name]
24. San Fernando Health Center, [name]
25. South Valley Health Center, [name]
26. Torrance Health Center, [name]
27. West Valley Health Center, [name]
28. Wilmington Health Center, [name]

PRÉCIS

Study Title

Precision Vaccine Promotion in Underserved Populations

Objectives

This will be a randomized clinical trial (RCT) to test the impact of text message innovations on receipt of influenza vaccination during the 2022-23 season.

Design

Interventions will be assigned randomly in a 2 x 2 factorial design to all patients eligible for vaccines, including a “standard of care” control group that will receive the standard DHS campaign message.

Interventions and Duration

The intervention period will include a 6-month flu season from 2022 –2023. This pilot study will be embedded as one arm of a larger trial. We will simultaneously test, using a comparative effectiveness trial design, the effect of the following 3 interventions, all compared to standard text messages: 1) Enhanced texting (with a callback by a trained call-center staff member to schedule a vaccine visit if the patient presses “1” in response to the text 2) Enhanced Bidirectional texting with a texting response from a trained call-center staff member who will help the patient schedule a vaccine visit through a series of back-and-forth texts 3) Provision of transportation information with information within the text messages that highlight to patients that MediCal will pay for transportation to a vaccine visit (Pilot arm).

Outcome Measures

Our primary outcome is the end of season influenza vaccination status based on California’s statewide vaccine registry (CAIR2). Secondary outcomes include vaccination intentions as measured by patients’ contact with appointment systems, scheduled vaccination appointments (and missed appointments), and influenza hospitalizations among patients that are eligible to receive vaccinations.

1. STUDY OBJECTIVES

1.1 Primary Objectives

The primary objectives are to 1) Conduct a Retrospective analysis of influenza and COVID-19 Messaging Strategies and Social Determinants of Non-Compliance. Between 2019 and 2021, DHS conducted a series of campaigns related to COVID and influenza vaccines with the objective of increasing community trust with geographically and demographically targeted advertisements. The 2021 campaign messages also adopted “Flu shot reserved for you” language that was found to be comparatively effective in Milkman et al., 2021.¹ We will also investigate disparities between the UCLA and DHS populations, 2) Develop Targeted Vaccination Promotion Approaches that Apply Principles of Behavioral Economics. We will use the results of Aim 1 to craft messages that (a) are consistent with evidence-based behavioral principles, and (b) promote “sludge reduction” mechanisms. These may include personalized messages about the easiest ways for patients to obtain free vaccinations - pharmacies closer to patients' homes and free transportation to healthcare facilities that have not been promoted at DHS in the past. Based on the retrospective analysis, we will vary the messenger identity and message content and tailor to specific subgroups. Additionally, we will use this time period to engage other large public service delivery systems that might participate in a proposal for a future multisystem RCT, 3) Conduct a Randomized Controlled Trial of Message Candidates in 2022-2023 Flu Season. The new messaging will be added to an ongoing RCT being conducted at DHS in a factorial design. The original study, limited to use of the patient portal to deliver messages, will be augmented with our approach and interventions, which will also incorporate paper mail, text messages, and call centers.

2. BACKGROUND AND RATIONALE

[figure not shown]
2.1 Background on Condition, Disease, or Other Primary Study Focus

Compliance with influenza and COVID-19 vaccinations is a critical public health issue, and underserved populations are vulnerable to community spread and frequently have more adverse outcomes. “Mega-studies” of insured populations with a history of vaccination may not be representative of heterogeneous groups of uninsured and underinsured patients. Reasons for noncompliance are multifactorial: well-meaning policies related to increasing vaccine accessibility may not be widely understood or disseminated, employer-based incentives and mandates may not be applicable, and issues related to communication, trust, and safety remain challenges and vary among different communities. This study will be the first large-scale randomized controlled trial testing personalized behavioral interventions in an underserved population. The Los Angeles County Department of Health Services (LACDHS) eligible population is as large as prior “Mega-studies”, though substantially less adherent to vaccination (currently 31.2% at LACDHS vs. 42% in Milkman et al.,) with a comparatively large proportion of Hispanic and Black patients.

3. STUDY DESIGN

See Figure 1 for study design of the larger randomized controlled trial. The pilot arm (this study) is illustrated in green.

Figure 1. Study design

4. SELECTION AND ENROLLMENT OF PARTICIPANTS

4.1 Inclusion Criteria

All patients over six months old that are members of an LACDHS managed care plan and have had contact with the health system in the past 2 years are eligible for LACDHS vaccination campaigns. In 2022, this includes over 273,000 patients.

4.2 Exclusion Criteria

The exclusion criterion is a patient age of < 6 months, as babies less than 6 months are not eligible for influenza vaccination. We will also exclude individuals who have already received their flu vaccination this season.

4.3 Study Enrollment Procedures

Randomized Controlled Trial. None of the proposed intervention strategies place patients at any additional risk of adverse outcomes, above and beyond the risks associated with routine immunization. Influenza vaccine is recommended by the Advisory Committee on Immunization Practices (ACIP) for the patient population included in this study and administration of these vaccinations is part of the routine practice of immunization delivery. Therefore, verbal agreement to administer vaccines (at the patient's medical office/clinic) will constitute their consent for vaccination, as is the accepted procedure for the administration of all routine vaccinations. As with all vaccinations offered in a doctor's office, patients are free to refuse vaccination.

For the randomized controlled trial, we will be requesting a waiver of consent. Our rationale is based on our contention that we meet the conditions as set forth in 45 CFR 46.116, subpart D, which asks that the researchers meet the following criteria: 1) the research involves no more than minimal risk to the subjects; 2) the waiver or alteration will not adversely affect the rights and welfare of the subjects; 3) the research could not practicably be carried out without the waiver or alteration; and 4) whenever appropriate, the subjects will be provided with additional pertinent information after participation. Further, all patients in the RCT will be within the covered entity of LACDHS. Regarding subject notification, given the intervention's focus on practice change and the anticipated very large number of patients from selected practices (tens of thousands), while we will update participating practices on the results of the intervention, we will not contact individual patients to notify them of the results. However, results will be made publicly available through presentations, publication, and other dissemination efforts.

5. STUDY INTERVENTIONS

5.1 Interventions, Administration, and Duration

Text messages will begin to be sent at the beginning of the 2022 flu season. We will randomly spread out the calls throughout the day and week in order to minimize unnecessary overload for the call center when patients text back a “1” response that they would like a

call or text message to help them. We can do this by randomizing patients into batches so that there is no systematic time-of-day or day-of-week for any patients. We will send up to 3 reminders this flu season.

Control arm: Standard Texts (n=232,950). Patient randomized to this study arm will receive up to 3 text messages, reminding them about the importance of influenza vaccination. The messages themselves are shown below. The standard texts will include a clinic call back number and patient portal self-scheduling for patients to schedule their influenza vaccines. The direct scheduling texts includes a direct number to an agent that can help schedule and answer questions on the phone in real time. The texts with a direct number to schedule will link a specified phone number to call and schedule. This number would be answered by a central agent quickly and a patient could schedule their flu shot at any clinic site. This specific phone number would not go through the multiple option menus a patient would normally experience when calling their clinic.

Intervention arm: Standard Texts with Transportation (n=3,050). The standard texts with transportation includes phone number for patients to reserve transportation to a vaccination appointment based on Medi-Cal health plan transportation resources.

Prepped Text Messages for DHS Flu Campaign 2022 - 2023

Standard Text:

#PCM#H: #FirstName#, your flu shot is ready! Call your clinic at #ExternalRefNo# or visit the LA Health Portal at <http://bit.ly/BookFluShot> if you want this shot held for you.

Standard Texts (+ Transportation)

#PCM#H: #FirstName#, your flu shot is ready! Call your clinic at #ExternalRefNo# or visit the LA Health Portal at <http://bit.ly/BookFluShot> if you want this shot held for you. You can call #Health Plan Phone Number# to schedule a free ride your flu shot through #Health Plan Name#

Examples (Transportation)

- Standard Texts (+ Transportation) - LA Care**

#PCM#H: #FirstName#, your flu shot is ready! Call your clinic at #ExternalRefNo# or visit the LA Health Portal at <http://bit.ly/BookFluShot> if you want this shot held for you. You can call [contact] to schedule a free ride for your flu shot through your LA Care health plan.

- Standard Texts (+ Transportation) - Health Net**

#PCM#H: #FirstName#, your flu shot is ready! Call your clinic at #ExternalRefNo# or visit the LA Health Portal at <http://bit.ly/BookFluShot> if you want this shot held for you can call [contact] to schedule a free ride for your flu shot through your Health Net health plan.

5.2 Handling of Study Interventions

As we will send up to 3 text messages during the flu season, we will search the EHR for whether or not the patient received an influenza vaccination this season. If yes, the patients will be dropped from the denominator of patients needing a text message reminder. We will search the EHR prior to each of the text message rounds. Review of medical records is needed in order to obtain the information about (a) influenza vaccination dates this upcoming season, and (b) address (in order to group patients into households as described above. We will review the EHR prior to each round of text messages to see if patients had received an influenza this season.

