6.2.2 Enrollment, Baseline, and/or Randomization

Enrollment

Identification of families (i.e., households): We will group families using one of two possible methods. First, LACDHS has an identifier that ties family members together. It is called the "Family Budget Unit." We will explore this method. If it does not work, we will use another method that we have utilized successfully in the UCLA-based study from which this study is derived. We will assume that people living in the same address belong to the same family. As a secondary measure, we use a

telephone number as a linking number (i.e., if two people have the same telephone number, we assume they are from the same household).

Baseline Assessments

Vaccination status. We will assess baseline vaccination status at the beginning of the flu season as we will exclude individuals who have already received their vaccination.

Randomization

We will randomly allocate families to one of the study arms shown above and send family members the allocated text message. All family members will therefore receive the same text message. This is meant to reduce confusion among patients. For the analysis, we will randomly select one index patient per household for analysis. This follows Cochrane criteria for being included in meta-analyses. We will attempt to affiliate index patients with practices, and randomize patients (families) within these practices.

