The retrospective analysis will result in a randomization and personalization template that will include placeholders and calculations for the following items: a) patient contact information, b) experimental group assignment, c) message contact dates (one per month in batches of 100 patients per day), d) randomly assigned message contact channel for each contact date (e.g. phone, portal, email, SMS), e) message templates with substitutable text, f) personalized message content for each month of messages, and g) stratification and personalization data elements identified in the retrospective analysis. These templates will be populated on premises at LACDHS with data to be retrieved by the Informatics Core staff. These randomized lists will be converted to personalized, tailored messages based on Mail Merge templates or similar DHS campaign management software. After lists and personalization have been completed, they will be approved by the research team in a final cross-check. All patients that have been vaccinated will be removed from contact lists before each wave of messages is delivered. These templated assignments may be moved from Excel to DHS Reporting Software (ELM) or other campaign management software by the Informatics Core.

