9.4 Outcomes

9.4.1 Primary outcome

End of season influenza vaccination status based on California's statewide vaccine registry (CAIR2).

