10. DATA COLLECTION AND QUALITY ASSURANCE

10.1 Data Collection Forms

Data will be collected from LACDHS electronic medical records and CAIR2 data.

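### Could influenza doses given before randomisation but missing from the EHR count as successes and dilute the transportation effect?

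*Combined protocol and SAP*

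**What the plan says.** **Eligibility.** Section 4.2 states: "We will also exclude individuals who have already received their flu vaccination this season". Section 6.2.2 repeats the intention: "We will assess baseline vaccination status at the beginning of the flu season as we will exclude individuals who have already received their vaccination". The schedule in 6.1 lists vaccination status at screening, on Day 1 (enrolment and randomisation), at intervention start, continuously, at intervention end and in follow-up. None of the three names the source of the information.

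**Reminder list.** Section 5.2 does name a source: "We will search the EHR prior to each of the text message rounds". Patients found vaccinated are "dropped from the denominator of patients needing a text message reminder". That governs who is texted, not who is analysed. Section 6.2.2 has the same rule without a source: "All patients that have been vaccinated will be removed from contact lists before each wave of messages is delivered".

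**Outcome.** Section 9.4.1 defines the primary outcome as "End of season influenza vaccination status based on" CAIR2. It gives no earliest date for a qualifying dose.

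**Data and analysis.** Section 10.1 says: "Data will be collected from LACDHS electronic medical records and CAIR2 data". It assigns neither source to a particular task. Under 10.2 one informatics group prepares both. Section 9.5 makes all analyses intention-to-treat, with a two-sided 0.05 level for the transportation comparison.

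**The concern.** Exclusion and outcome may rest on different records. Suppose the baseline check used only the EHR, and the EHR did not hold doses given outside the health system. A patient vaccinated at an outside site before randomisation would then pass the check, be randomised, and appear as vaccinated in CAIR2 at the end of the season. No text could have changed that result.

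Two things would be at stake. The analysed population would include people whom 4.2 means to leave out, and the observed effect would be smaller than the effect among patients who could still respond. With only 3,050 patients in the transportation arm, there is little power to give away.

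**Working it through.** **Inputs from the documents.** Control n = 232,950 and transportation n = 3,050 (5.1); two-sided α = 0.05 (9.5); effect 2%, read as 2 percentage points (9.2); control rate 31.2% (2.1, because 9.2 gives none).

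**Assumptions.** Everyone randomised is analysed. The share f of patients vaccinated before randomisation but unseen by the check is not in the documents, so a range is shown.

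**Step 1: the plan's own figure.** For the pooled two-proportion test, power = Φ[(d − 1.960 × SE₀)/SE₁], with SE₀ from the pooled rate and SE₁ from the separate rates.
- Pooled rate = (232,950 × 0.312 + 3,050 × 0.332)/236,000 = 0.3123
- SE₀ = 0.008446; SE₁ = 0.008581
- Power = Φ[(0.02 − 0.016554)/0.008581] = Φ(0.402) = 65.6%

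The 80% in 9.2 is not reproduced with these inputs. The shortfall is present at f = 0, so early doses do not cause it.

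**Step 2: what missed early doses do.** Let p_C and p_T be the vaccination rates among patients still unvaccinated at baseline. Randomisation gives both arms the same expected f.
- Observed control rate = f + (1 − f)p_C
- Observed transportation rate = f + (1 − f)p_T
- Observed difference = (1 − f)(p_T − p_C)

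If the texts do nothing, p_T = p_C and the observed difference is (1 − f) × 0 = 0. The test is unbiased under the null.

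**Step 3: size.** Take 31.2% as the whole-season rate, early doses included, and a 2-point effect among patients still unvaccinated. Unfiltered power uses d = 0.02(1 − f). At f = 1% this is Φ[(0.0198 − 0.016554)/0.008580] = Φ(0.378) = 64.7%. Removing the early doses gives arm sizes n(1 − f), control rate (0.312 − f)/(1 − f) and d = 0.02. The second column is f/0.312.

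| f | Share of all vaccinations | Observed difference (points) | Power, no filter | Loss from 65.6% | Power, early doses removed |
|---|---|---|---|---|---|
| 0.5% | 1.6% | 1.99 | 65.2% | 0.4 | 65.6% |
| 1% | 3.2% | 1.98 | 64.7% | 0.9 | 65.7% |
| 2% | 6.4% | 1.96 | 63.9% | 1.7 | 65.8% |
| 5% | 16.0% | 1.90 | 61.2% | 4.4 | 66.4% |
| 10% | 32.1% | 1.80 | 56.7% | 8.9 | 68.4% |

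**Step 4: other readings of the inputs.**
- If 31.2% is the rate among patients still unvaccinated, power without and with the filter is 62.9% and 64.7% at f = 2%, 59.0% and 63.4% at 5%, and 52.9% and 61.1% at 10%.
- If the 2 points already refer to everyone randomised, power without the filter stays at 65.6%. With it, power is 66.6%, 67.5%, 70.8% and 77.1% at f = 1%, 2%, 5% and 10%.

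**Step 5: which f is plausible.** Section 5.1 starts the texts at the beginning of the season, and 6.2.2 places the baseline check there too, so the window for early doses is short. The lower rows need 16% to 32% of the season's vaccinations to fall before randomisation and also escape the check. Nothing in the documents supports that.

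**The case for a change.** The best case for a change is that it is cheap and never hurts. Two sentences and a date filter on data already being obtained would tie the analysed population to 4.2 and give the outcome a start date. The filter raised power in every scenario tried. It is also compatible with intention-to-treat, because a dose dated before allocation is a baseline characteristic and can be applied identically in all arms. The exclusion in 4.2 itself expects some patients to be vaccinated before enrolment, and power is already below the stated figure.

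Much of this stands. The source is unnamed, the dose window is unwritten, and the documents do not say whether the EHR receives outside doses. But silence fits a check against both sources as well as a check against the EHR alone. Read with 4.2 and 6.2.2, the end-of-season outcome already means vaccination after a baseline at which the patient was unvaccinated. The power shortfall belongs to 9.2 and lends no weight here. The filter is also incomplete: doses given between randomisation and a delayed first text stay in the comparison. Finally, the effect among everyone the campaign would text is itself a legitimate pragmatic target, so part of the so-called dilution is a choice of estimand.

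**Conclusion.** No change to the plan follows. Followed as written, it excludes patients already vaccinated, assesses status at screening and Day 1, and gives a valid intention-to-treat comparison. Harm needs three things that the documents do not establish: an EHR that misses outside doses, a baseline check confined to the EHR, and many such doses before randomisation. Even then no arm is favoured and the type I error is unaffected.

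The likely cost is small: 0.9 of a power point at f = 1% and 0.4 at f = 0.5%, on the whole-season reading of 31.2% with both arms fully analysed. If the arm sizes count patients rather than one index patient per household (6.2.2), the absolute power figures would be lower, but the factor (1 − f) would not change.

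What remains is missing detail that analysts holding both CAIR2 and EHR data would probably fill sensibly. Stating the baseline source and the dose window in the analysis documentation would be a courtesy to readers, not a correction.

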5.3 Adherence Assessment

In order to ensure that the study interventions are being reliably delivered we will implement a series of test messages to the study team to ensure fidelity of the messages to the study design and DHS communication quality standards prior to RCT implementation. Study staff will conduct assessments regularly during the intervention to ensure that tests do not fail.

6. STUDY PROCEDURES

6.1 Schedule of Evaluations

Assessment	Screening: Baseline	Baseline, Enrollment, Randomization: (Day 1)	Intervention Start (Month 1)	Continuously Measured or monitored	Intervention End (Month 6)	Follow-up Period
Patient-level assessments						
Demographics	X					
Vaccination status	X	X	X	X	X	X

Scheduled vaccine appts			X	X	X	
Missed vaccine appts			X	X	X	
Influenza hospitalizations			X	X	X	
Adverse Events			X	X	X	

6.2 Description of Evaluations

6.2.1 Screening Evaluation

Consenting Procedure

For the randomized controlled trial, we will be requesting a waiver of consent. Our rationale is based on our contention that we meet the conditions as set forth in 45 CFR 46.116, subpart D, which asks that the researchers meet the following criteria: 1) the research involves no more than minimal risk to the subjects; 2) the waiver or alteration will not adversely affect the rights and welfare of the subjects; 3) the research could not practicably be carried out without the waiver or alteration; and 4) whenever appropriate, the subjects will be provided with additional pertinent information after participation. Further all patients in the RCT will be within the covered entity of LACDHS. Regarding subject notification, given the intervention's focus on practice change and the anticipated very large number of patients from selected practices (tens of thousands), while we will update participating practices on the results of the intervention, we will not contact individual patients to notify them of the results. However, results will be made publicly available through presentations, publication, and other dissemination efforts.

